Dose Justification: Immunologic testing in mice indicates that there is no difference in antibody responses to P10s in mice between the 300 µg and 500 µg dose (GLP Report: “Determination of the Safety and Tolerability of Immunization with LeY Peptide Mimotope Vaccine in Mice”). Dose escalation is meant to test the safety of the preparation in terms of its non-immunological toxicity. In this case the assumption is that the putative adverse effects increase monotonically with the dose, and exploring the higher-than-necessary doses ensures safety of the lower ones. As for the immunological effects, they are characteristically non-monotonic with an optimal effect in a specific dose range, and weaker effects and even induction of tolerance for doses much higher or lower than the optimal one. Thus, the classical dose escalation trial may or may not detect the immunological effects, including adverse autoimmune phenomena. A dose-escalation algorithm better suited for determining the immunological impact should include both increasing and decreasing arms, and should be terminated when doses beyond the one that leads to optimal immunological effect are reached, provided they are tolerated otherwise. When increasing immunological effect is detected in one of the arms, the other one may be discontinued, if not necessary for the toxicology study.

4. Trial Objectives

a. Primary Objective – Safety: The safety and tolerability of the P10s-PADRE/ MONTANIDE™ ISA 51 VG vaccine will be determined by toxicity assessments throughout the duration of the study. Subjects will be evaluated for toxicity using the National Cancer Institute (NCI) Common Terminology Criteria for Adverse Events (CTCAE) Version 4.0. A toxicity of Grade 3 or higher will be considered a dose limiting toxicity (DLT).

b. Secondary Objectives – Immune Response:

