- b. Dose Assignment:** The decision to escalate or de-escalate the dose, expand the cohort or terminate the study will be based on assessment for DLT, which will require 9 weeks per subject. The time to assess a cohort of 3 for DLTs and immune responses is thus anticipated to be 13 weeks based on an accrual rate of 2 eligible Stage IV subjects per month.
- c. Specimen Handling:** A trained phlebotomist or registered nurse will draw the blood required for clinical and research purposes. Research specimens will be delivered to [name] research laboratory.
- d. Visit Breakdown:**

Pre-study Visit

- Complete medical history and physical examination
- Complete blood count with differential
- Other blood tests include:
 - Collection of serum samples used to measure the immune response to the vaccine.
 - SGOT (Serum glutamic-oxaloacetic transaminase)
 - Alkaline Phosphatase Level
 - LDH (lactate dehydrogenase)
 - GGT (gamma-glutamyl transferase)
 - Creatinine
 - Calcium
 - Albumin
 - Amylase
 - TSH (thyroid stimulating hormone)
 - T₄
 - ANA (Anti-nuclear antibody)
 - Bilirubin
 - PT/PTT
- Concomitant medications will be collected from registration to end of treatment.
- Serum pregnancy test for women of childbearing potential.
- Study lab samples. Up to 40 mLs of blood will be collected in red and purple tubes for circulating tumor cell evaluation, TACA (tumor associated carbohydrate antigens) assessment, and immune effector assays.

- DTH Skin Test to test the subjects' immunocompetency. Trichophyton Antigen and the Candida antigen will be administered intradermally (id) as control antigens at separate locations on the subject's back, and the resulting induration will be read 48– 72 hours later.
- CTC (circulating tumor cells) response to the vaccine will be measured in serum samples drawn to determine the presences of CTCs pre- and post-mimotope administration.

48 – 72 hours after Pre-Study Visit

- DTH Skin Test Reading

48 hours prior to dosing

- Serum pregnancy test for women of childbearing potential.

Week 1

- Administration of the P10s-PADRE/MONTANIDE™ ISA 51 VG vaccine. The vaccine will be administered subcutaneously (SC) by nurses in the Infusion Center at the Cancer Institute.
- Post vaccine administration, the following vital signs will be monitored every 15 (+/- 5 minutes) minutes for one hour: blood pressure, temperature, and pulse.
- Complete medical history and physical examination

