- f. **Dose Limiting Criteria:** Subjects who develop any grade 3 or greater toxicity as per NCI CTCAE v. 4 toxicity criteria, Grade 2 or greater autoimmune toxicity with the exception of vitiligo, or Grade 2 or greater hypersensitivity reactions will be treated and referred for additional care as indicated with systemic steroids, topical steroids, epinephrine or Benadryl. These subjects will be removed from the study and will be followed as per protocol defined monitoring and/or until resolution of toxicity.
- g. **Dose Assignment:** Subjects will be treated with vaccine admixed with MONTANIDE™ ISA 51 VG on weeks 1, 2, 3, 7 and 19 in cohorts according to the following dosing diagram:

DLT and the immune-response endpoints are defined in Section 4, “Trial Objectives”. Upon evaluation of all subjects in a cohort (3 or 6 per dose level), the decision whether to escalate, de-escalate or stop will proceed according to the cohort-appropriate schedule shown in **Tables 1, 2, and 3**.

Table 1: Toxicity Decision Rules for Initial Cohort (300 µg Vaccine Dose)

DLTs/ Cohort¹	Action
0/3	Begin accrual to Escalation Cohort
1/3	Expand Initial Cohort to 6 subjects
1/6	Begin accrual to Escalation Cohort
2/6, 3/6, or 4/6	Begin Accrual to De-Escalation Cohort
2/3 or 3/3	Begin Accrual to De-Escalation Cohort

¹ DLT = Dose-Limiting Toxicity

Table 2: Toxicity Decision Rules for Escalation Cohort (500 µg Vaccine Dose)

DLTs/ Cohort¹	Action
0/3 or 1/3	Expand cohort to 6 subjects
1/6	Stop: Declare escalation dose to be MTD ²
2/6, 3/6, or 4/6	Stop: Previous dose level is MTD ²
2/3 or 3/3	Stop: Previous dose level is MTD ²

¹ DLT = Dose-Limiting Toxicity² MTD = Maximum Tolerated Dose**Table 3: Toxicity Decision Rules for De-Escalation Cohort (100 µg Vaccine Dose)**

DLTs/ Cohort¹	Action
0/3 or 1/3	Expand cohort to 6 subjects.
1/6	Stop: De-escalation dose level is the MTD ²
2/6, 3/6, or 4/6	Stop: De-escalation dose level is above MTD ²
2/3 or 3/3	Stop: De-escalation dose level is above MTD ²

¹ DLT = Dose-Limiting Toxicity² MTD = Maximum Tolerated Dose

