If the initial-cohort dose of 300 µg P10s-PADRE is declared to be the MTD and only 3 subjects were enrolled into the initial cohort, then this cohort will be expanded to 6 to assure that 6 subjects are treated at the MTD. The CRA for the trial will assign the subjects to cohorts and communicate the assignments to the research nurse, who will communicate them to the investigator. Only one cohort will be open to enrollment at a time. After the last non-boost dose in each cohort, the study will have a 3-week hold pending the cohort's DLT evaluation. Staggered dosing for the first two patients within each cohort will allow an interval of one week observation for toxicity following the first injection in the previous patient. The research pharmacist will be notified by orders of the registration and cohort dose. Expansion of the cohort to 6, or enrollment to the next cohort, may start once the previous 3 subjects complete their week-9 serology and are evaluated for DLT. Subjects who withdraw from the dose-escalation study without a DLT will be replaced. Subjects who withdraw from the dose- de-escalation study without a DLT will be replaced. Subjects who withdraw with a DLT will be considered evaluable for MTD determination.

8. Risks and Toxicities To Be Monitored

a. Potential Toxicities, Risks and Precautions:

Procedure	Risks	Measures to Minimize Risks
Complete history and physical exam, including blood chemistries	Identification of previously unknown condition	Qualified health care provider to evaluate potential subject Research records are kept in a locked area accessible only by study personnel.

Procedure	Risks	Measures to Minimize Risks

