Subjects will receive up to 5 planned vaccine doses unless they withdraw from the study or develop a dose limiting event as stated above, at which time they will discontinue the injections and be removed from the study. There will be no dose modifications for toxicity. Special attention will be given to toxicities mediated by autoimmune mechanisms, such as colitis, thyroiditis or systemic lupus erythematosus (SLE), as well as to injection-site local reactions or allergic reactions. The NCI CTCAE Version 4.0 will be used for toxicity and SAE reporting. A copy of the CTCAE Version 4.0 can be downloaded from the Cancer Therapy Evaluation Program (CTEP) home page or viewed in **APPENDIX A**. All appropriate treatment areas have access to a copy of the CTCAE Version 4.0.

Any subject may voluntarily revoke consent and withdraw from the study at any time. A subject may be terminated early for the following conditions: (i) non-compliance, (ii) an unrelated intercurrent illness that may affect assessment or place the subject at risk for AEs or require systemic steroids, (iii) deterioration in performance status so as to make participation a hardship for the subject, (iv) for toxicity as determined by the DLT criteria, or (v) for any reason that the investigator feels it is not in the subject's best interest to continue.

- b. Benefits:** As this is the first time Mimotope P10s-PADRE will be administered to humans, there are no clearly defined benefits to subjects of this study. However, this vaccine may potentiate an immune response which could improve median progression-free survival and overall survival of cancer patients.
- c. Injury:** For DOD-funded research, participants can receive medical care at an Army hospital or clinic free of charge. If participants pay out-of-pocket for medical care elsewhere for injuries caused by this research study, they should contact the Principal Investigator. If the issue cannot be resolved, contact the U.S. Army Medical Research and Materiel Command (USAMRMC) Office of the Staff Judge Advocate (legal office) at [contact]/[name]

9. Specimen Handling

Samples will be stored in the UAMS Tissue Procurement Facility, located in room B.018 of the hospital. Cryotubes that contain specimens will be labeled with barcodes. The coded number is linked to patient identification and time of blood draw. Specimens will be stored frozen at -80°C

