⁵The DTH skin test at prestudy will test the subjects' immunocompetency. Control antigens, Trichophyton Antigen and Candida antigen, will be administered id and the resulting induration will be ready at 48 - 72 hours post injection.

⁶ The DTH skin tests on weeks 5, 9 and 21 will test the DTH response to Mimotope P10s-PADRE. Trichophyton Antigen and Candida antigen will be administered id alongside Mimotope P10s-PADRE as control antigens to assess immunocompetency. DTH skin test indurations will be read at 48 – 72 hours post injection.

⁷ Visits must occur at set time points mentioned in the study calendar (+/- 3 days) with the exception of reading the skin test which must occur 48-72 hours post administration.

⁸ Concomitant medications will be collected from registration to end of treatment.

⁹ Post vaccine administration, the following vital signs will be monitored every 15 minutes (+/- 5 minutes) for one hour: blood pressure, temperature, and pulse.

¹⁰ Follow up visits shall begin with the next scheduled standard of care appointment and then shall occur every six months for five years and then yearly until death.

11. Criteria for Evaluation

Primary Objective – Safety:

- **Determination of DLT:** See Section 8, “Risks and Toxicities to be Monitored”. Any event that meets the dose limiting criteria will be determined a dose limiting toxicity.

Secondary Objectives – Immune Response:

- **Immunological Evaluation:** Serum will be collected at the Study Lab time points indicated in the study calendar in Section 10. Samples will be collected and stored by the UAMS Cancer Institute Tissue Bank following established Tissue Bank SOPs. IgM and IgG titers to TACAs will be evaluated by ELISA on TACA adhered to plates and FACS analysis of TACA adhered to liposomes. A positive TACA-directed immune response will be defined as an anti-TACA serum antibody titer of 1:40 for a baseline pre-vaccination titer of 0 or a \geq 4-fold increase over baseline titer > 0 (1, 11). Subjects will be judged to have had an adequate immune response if they have a positive TACA-directed immune response at any one of the first five designated time points following vaccine administration (Weeks 2, 3, 4, 7 and 9). The value of a booster immunization will be determined by anti-TACA IgM and IgG titers obtained from study labs collected on week 21.

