a. Sample Size, Study Duration and General Considerations: Because each subject will receive multiple vaccine injections at a constant dose over an extended period of time, the second and third subject of *the same* dose cohort will be enrolled, as available, before the first subject has finished all scheduled injections. However, if two or more subjects are enrolled on the same day, then their injection schedules will be staggered at least one week apart. The decision to escalate or de-escalate the dose, expand the cohort, or terminate the study will be based on assessment for DLTs, which will require 9 weeks per subject. Upon evaluation of all subjects in a cohort (3-6/dose), dose escalation will proceed according to the schedule shown in **Tables 1, 2, and 3**. Except for the fact that they allow for possible de-escalation from the initial dose of 300 μ g, **Tables 1, 2, and 3** constitute the toxicity-based “traditional” design of Storer (43). The time to assess a cohort of 3 for DLTs is anticipated to be 13 weeks based on an accrual rate of 2 eligible Stage IV subjects per month. If no DLTs occur in the initial and final cohorts, then this study will require nine subjects. Subjects who withdraw from the dose-escalation study without a DLT will be replaced. Subjects who withdraw from the dose-de-escalation study without a DLT will be replaced. Subjects who withdraw with a DLT will be considered evaluable for MTD determination. Given the recruitment and immunization/evaluation schedule, we expect this study to be completed in a minimum of 12 and a maximum of 24 months.

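### Does the plan's silence on DLTs at or after the Week-19 booster leave the MTD undetermined?

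*Combined protocol and SAP*

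**What the plan says.** Three places set the timing of dose decisions.

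- Section 7b: the decision "will be based on assessment for DLT, which will require 9 weeks per subject". Section 12a repeats this almost word for word ("will be based on assessment for DLTs, which will require 9 weeks per subject") and adds that the time to assess three subjects "is anticipated to be 13 weeks based on an accrual rate of 2 eligible Stage IV subjects per month".
- Section 7g, after Table 3: expansion to six or opening the next cohort "may start once the previous 3 subjects complete their week-9 serology and are evaluated for DLT".
- Section 7g also imposes a three-week hold after the final dose before the booster, while the cohort's DLTs are evaluated.

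Other places describe the event without an end date.

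- Section 7g, introducing Tables 1 to 3: "DLT and the immune-response endpoints are defined in Section 4".
- Section 4a: safety "will be determined by toxicity assessments throughout the duration of the study".
- Section 8a: "Subjects will receive up to 5 planned vaccine doses unless they withdraw from the study or develop a dose limiting event as stated above".
- Section 11: "Any event that meets the dose limiting criteria will be determined a dose limiting toxicity".

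Sections 7g and 12a also make a subject who leaves with a DLT evaluable for the MTD, with no time limit. Section 12b reports every toxicity by type, severity and dose number at onset, and the number and proportion of subjects with a DLT in each cohort.

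**The concern.** A subject's DLT assessment ends well before her booster, so Tables 1 to 3 rest on four of the five planned doses. The plan discloses this. What looks like a hole is that a Grade 3 event after the booster is a DLT under Sections 4a and 11, and no passage says whether it enters the table count, bears on a decision already made, or is only reported.

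The question could arise while decisions are still pending. Suppose a 500 µg cohort has one DLT by Week 9 among its second three subjects and one booster DLT among its first three, both known at the decision. A nine-week count gives 1/6, and Table 2 names the escalation dose as the MTD. A count over all time gives 2/6, and Table 2 names the previous level. Similarly, a 300 µg booster DLT could turn 0/3 into 1/3 in Table 1 after 500 µg accrual has opened. The MTD is the main safety conclusion, so two counts for the same data would matter.

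**Working it through.** **The plan's own figure.** Section 12a gives 2 subjects a month and 9 weeks each. With a four-week month the gap is 2 weeks, entries are at weeks 0, 2 and 4, and the third subject is assessed at 4 + 9 = 13 weeks, as stated. With calendar months the gap is 52.18/12/2 = 2.17 weeks, giving 2 × 2.17 + 9 = 13.3 weeks.

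**What the nine weeks cover.** Counting the first dose as week 0, the Week-7 dose falls at 6 weeks. Adding the three-week hold in Section 7g gives 6 + 3 = 9, the period in Sections 7b and 12a. If Week 7 means seven weeks after entry, the sum is 10 and the booster is at 19 rather than 18. Either way the assessment ends nine weeks before the booster. The three timing passages agree with one another.

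**Where boosters fall against a six-subject decision** (gap of 2 weeks, next three subjects entering from week 13):

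| Event | Weeks from first entry |
|---|---|
| First three: boosters (entry + 18) | 18, 20, 22 |
| First three: Week-21 visits (entry + 20) | 20, 22, 24 |
| First three: Week-24 visits (entry + 23) | 23, 25, 27 |
| Second three: entry | 13, 15, 17 |
| Six-subject decision | 17 + 9 = 26 |

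For a gap of g weeks the last of these boosters is at 2g + 18 and the decision at 4g + 18, so the dose is never later than the decision. That concerns dosing, not results. The third Week-24 visit (27) follows the decision (26). With g = 1 the third Week-21 visit (2 + 20 = 22) falls on the decision day (4 + 18 = 22). With random arrivals at 2 a month, Week k counted as k weeks after entry and no hold, all three boosters precede the decision in 98.9% of simulated cohorts, all Week-21 visits in 83.8% and all Week-24 visits in 48.0%.

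**Chance of moving 1/6 to 2/6 or more, if booster DLTs were counted.** Two or three first-block subjects are boosted, because a subject with a DLT is removed. For booster risk b (assumed) the chance is 1 − (1 − b)² or 1 − (1 − b)³:

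| b | two boosted | three boosted |
|---|---|---|
| 2% | 0.04 | 0.06 |
| 5% | 0.10 | 0.14 |
| 10% | 0.19 | 0.27 |

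**The 0/3 path.** The 300 µg boosters at weeks 18 to 22 overlap with 500 µg dosing (weeks 13 to 17 + 6 = 23). With the same assumed risk p at each of five doses, the chance of 0/3 by Week 9 followed by at least one 300 µg booster DLT is (1 − p)¹² × [1 − (1 − p)³]: 0.026, 0.046 and 0.077 at p = 1%, 2% and 5%. No MTD row changes here. If 500 µg fails, Section 7g expands a three-subject 300 µg cohort to six in any case.

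**Whole trial.** Simulating Tables 1 to 3 on the nine-week count, with 0/6 taken as passing and all subjects boosted, a known booster DLT would change a six-subject row in about 0.7%, 2.2% and 7.8% of trials. Either situation arises in about 3%, 7% and 14%. At the two lower risks most of that is the 0/3 path. A 5% risk per dose already implies 1 − 0.95⁴ = 18.5% with a DLT by Week 9.

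**The case for a change.** The best case for a change is that a nine-week assessment is a duration, not an instruction to disregard a DLT already known at the decision. Section 7g sends the reader to Section 4, where toxicity is followed throughout, and a subject leaving with a DLT counts for the MTD without a time limit. Safety reviews do not fill the gap: the suspension and stopping triggers in Section 17b are study-wide, and one or two non-fatal Grade 3 booster events alone would not meet them. For a six-subject 500 µg cohort on the 0/3 path, the review after the cohort completes comes at about week 30 + 23 = 53, after the decision at 30 + 9 = 39. A clarifying sentence would be cheap.

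The silence is real, and that much stands. The rival count is strained, however. Section 7g refers to Section 4 for what a DLT is; Sections 7b, 7g and 12a say when the tables are read. The evaluability sentence follows the sentences on replacing subjects who withdraw without a DLT, and settles who is replaced rather than how long events are counted.

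Oversight is also wider than the formal triggers. Section 8a has the Medical Monitor reviewing all toxicities regularly. On the 0/3 path, the Section 17b review of the completed 300 µg cohort comes at about week 4 + 23 = 27, some 12 weeks before the six-subject 500 µg decision at week 39.

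**Conclusion.** This is missing detail that analysts can fill sensibly, and it calls for no change. Followed as written, the plan gives a coherent MTD statement based on the nine-week assessment, and safety is reported over the whole study. A DLT at or after Week 19 does not disappear: Section 12b lists it by dose number and includes it in the cohort's DLT figures. With 9 subjects if no DLTs occur and a goal of 18, the split before and after the booster can be read directly, so separate Week-9 and full-study columns would only rearrange the same information.

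Counting known booster DLTs would change a six-subject row in roughly 1%, 2% or 8% of trials at assumed per-dose risks of 1%, 2% and 5%. Those risks are not in the documents, and the figures take every subject as boosted; missed boosters lower them. Whether first-block booster follow-up is complete at a decision depends on accrual: dosing would normally be done, but the Week-24 visits often would not. The sponsor may add a sentence on how late DLTs relate to the tables, but the analysis does not depend on it. Nothing here judges whether nine weeks is clinically the right period.
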